### **OVERVIEW OF STUDY DESIGN**

This is a global, multicenter, blinded, LTFU study to evaluate the incidence of the clinical diagnosis of asthma and the frequency of wheezing in infants and children (otherwise healthy or with underlying comorbidities for severe RSV) who have completed their treatment course and their last study-related visit in a previous Phase 2 study, 64041575RSV2004, in which they received lumicitabine or placebo for the treatment of RSV infection. Subjects will be followed for at least 2 years following treatment. This study may be extended up to an additional 3 years (ie, total duration up to 5 years after randomization into Study 64041575RSV2004). Participation in this LTFU study is optional for study sites. This LTFU study will be offered to subjects of Study 64041575RSV2004 if their site decides to participate in this LTFU study.

Subjects will be enrolled within 3 months after randomization in Study 64041575RSV2004.

No study drug will be administered in this study. The parent/caregiver of the subject and the investigator will remain blinded to the study treatment (lumicitabine or placebo) administered in Study 64041575RSV2004 until the completion of this LTFU study, including any extension period.

Assessments will be performed at the study site at enrollment in this study and at 3, 6, 12, 18, and 24 months after entry visit in Study 64041575RSV2002. The last visit of Study 64041575RSV2004 (ie,

Day 28) may be combined with the entry visit of this LTFU study. The same assessments will be performed during monthly phone calls with the parent/caregiver between the study site visits.

An unblinded interim analysis will be performed when all subjects from the first season in Study 64041575RSV2004 who are enrolled in this LTFU study complete the 18 month follow-up assessment of this LTFU study. This interim analysis will serve to evaluate the need for an extension of the follow-up period.

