**TIME AND EVENTS SCHEDULE**

Study Period	Entry Visit a,b	Assessment Period b				
	Months	0	3 (±7 days)	6 (±7 days)	12 (±7 days)	18 (±7 days)
Screening/Administrative						
Informed consent	X					
Eligibility criteria	X					
Baseline demographics c	X					
Medical and family history c,d	X					
Wheezing and medication parent/caregiver card distribution and verification e,f	X	X	X	X	X	X
Clinical Evaluations						
Clinician questionnaire g	X	X	X	X	X	X
	Monthly telephone calls between study site visits h					
Collection of data from lung function tests and allergy tests (immunoglobulin E and skin tests) i			X			
Medical resource utilization j			X			
Medication l			X			
Safety Evaluations						
Serious/reportable adverse events k			X			

- a. The entry visit needs to take place within 3 months after randomization in Study 64041575RSV2004. The last visit of Study 64041575RSV2004 (ie, Day 28) may be used as the entry visit for this study.
- b. Assessments will be performed during study site visits (entry visit and 3, 6, 12, 18, and 24 months after entry visit in Study64041575RSV2002) and during monthly telephone calls with the parent/caregiver between study site visits.
- c. Baseline demographics and medical/family history from the previous Phase 2 Study 64041575RSV2004 will be captured in the long-term follow-up electronic case report form (eCRF).
- d. Medical and family history to identify risk factors for wheezing/asthma at baseline, including prenatal smoking by the subject's mother, subject's exposure to tobacco smoke, wheezing associated with symptoms of acute respiratory infections, whether the subject has siblings or attends kindergarten/day care, and personal and/or family history of atopy/allergy will be recorded in the eCRF.
- e. Parents/caregivers will be provided with a wheezing parent/caregiver card to be completed daily. The information recorded on the wheezing parent/caregiver card will aid the site responsible person to complete the clinical questionnaire when interviewing the subject's parent/caregiver. Parents/caregivers will be required to return the completed parent/caregiver cards to the study sites every 3 months (eg, in person or by mail/email/fax when no study site visit is scheduled).

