### **9.1.3. Study Period**

No study drug will be administered.

The medical follow-up of the subjects will be performed according to the local standard of care during the assessment period.

At each study site visit (3, 6, 12, 18, and 24 months after entry visit) as noted in the [Time and Events Schedule](#) and during a monthly telephone call (calendar month  $\pm 7$  days), a clinical questionnaire (see [Attachment 2](#)) will be completed by a study site responsible person, by interviewing the subject’s parent/caregiver, to collect the following information:

- Wheezing.  
The parent/caregiver will be provided with a wheezing parent/caregiver card to be completed daily (see [Attachment 3](#)) which will aid the site responsible person in completing the questionnaire.
- Diagnosis of asthma, eczema, and allergic rhinitis. All medical information needed to confirm the diagnosis of asthma, eczema, and allergic rhinitis needs to be collected by the study site personnel.
- Impact of the subject’s health status on normal daily activities for subjects, parents/caregivers, and other family members.

Medical resource utilization data will be collected throughout the study.

Parents/caregivers will also be provided with a medication parent/caregiver card to record medication use on a daily basis (see [Attachment 4](#)).

Parents/caregivers will be required to return the completed wheezing and medication parent/caregiver cards to the study sites every 3 months (eg, in person or by mail/email/fax when no study site visit is scheduled).

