## **10. SUBJECT COMPLETION/WITHDRAWAL FROM THE STUDY**

### **10.1. Completion**

A subject will be considered to have completed the study if he or she has completed assessments at Month 24 of the assessment period (or until the last assessment, if the study is extended).

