1.2. Trial Design

This is a global, multicenter, blinded, LTFU study to evaluate the incidence of the clinical diagnosis of asthma and the frequency of wheezing in infants and children (otherwise healthy or with underlying comorbidities for severe RSV) who have completed their treatment course and their last study-related visit in a previous Phase 2 study, 64041575RSV2004, in which they received lumicitabine or placebo for the treatment of RSV infection. Subjects will be followed for at least 2 years following treatment. This study may be extended up to an additional 3 years (i.e., total duration up to 5 years after randomization into Study 64041575RSV2004). Participation in this LTFU study is optional for study sites. This LTFU study will be offered to subjects of Study 64041575RSV2004 if their site decides to participate in this LTFU study.

Subjects will be enrolled within 3 months after randomization in Study 64041575RSV2004.

No study drug will be administered in this study. The parent/caregiver of the subject and the investigator will remain blinded to the study treatment (lumicitabine or placebo) administered in Study 64041575RSV2004 until the completion of this LTFU study, including any extension period.

Assessments will be performed at the study site at enrollment in this study and at 3, 6, 12, 18, and 24 months after randomization in Study 64041575RSV2004. The last visit of Study 64041575RSV2004 may be combined with the entry visit of this LTFU study. The same assessments will be performed during monthly phone calls with the parent/caregiver between the study site visits.

More details can be found in the Time-and-Event schedule in the study protocol.

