5. EFFICACY

5.1. Primary Efficacy Endpoint(s)

5.1.1. Definition

The primary endpoints are:

1. Clinical diagnosis of asthma within the first 2 years after the RSV infection, as diagnosed by a physician and reported by the parent/caregiver. This will be derived based on the completed study questionnaires at each visit/telephone call until the final visit. It is either “Yes” or “No”.
2. The percentage of wheezing days in a subject within the first 2 years after the RSV infection will be calculated as:

$$\text{Percentage of wheezing days} = \left(\frac{\text{number of wheezing days}}{\text{day of study completion} - \text{day of informed consent} + 1} \right) * 100$$

The percentage will be rounded to the nearest integer. Number of wheezing days is the sum of all days that were reported in the Monthly visit reports. The day of informed consent is the informed consent of the RSV2002 study.

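### The primary wheezing formula in SAP 5.1.1 carries a 2-year label but has no 2-year end date, and protocol and SAP anchor the visits differently

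*SAP*

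**What the plan says.** **The endpoint.** SAP 5.1.1 opens the wheezing definition with "The percentage of wheezing days in a subject within the first 2 years after the RSV infection will be calculated as". The denominator is the day of study completion minus the day of consent, plus 1, and the SAP specifies that "The day of informed consent is the informed consent of the RSV2002 study". The numerator is the sum of all wheezing days in the monthly visit reports. The result is rounded to a whole percent. The only analysis phase (SAP 2.1, Table 1) ends at last contact, so it supplies no 2-year limit either.

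**The protocol schedule.** Footnote a of the Time and Events Schedule says "The entry visit needs to take place within 3 months after randomization in Study 64041575RSV2004". The last RSV2004 visit, Day 28, may serve as the entry visit. The synopsis places site visits "at 3, 6, 12, 18, and 24 months after entry visit in Study 64041575RSV2002", and Section 9.1.3 agrees. Under Section 10.1 a completer has "completed assessments at Month 24 of the assessment period".

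**The SAP schedule.** SAP 1.2 places the same visits "at 3, 6, 12, 18, and 24 months after randomization in Study 64041575RSV2004". SAP 2.5 numbers the monthly reports from Month 2, to reflect time since the RSV event.

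**Related endpoints.** The asthma definition states the 2-year limit, but its source sentence says only that it is "derived based on the completed study questionnaires at each visit/telephone call until the final visit". Table 2 counts the 2-year wheezing episodes from consent to the last day in the trial for completers. Table 3 stops eczema and allergic rhinitis at the Month 24 analysis visit.

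**The concern.** The label sets a period that the formula does not apply. The label is not merely another name for follow-up: the primary objective, in both documents, asks for results that fall during follow-up and also within 2 years of the infection. The formula enforces only the first condition.

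Under the protocol schedule, the amount of time counted beyond 2 years equals the child's delay from randomization to entry. Two children with the same wheezing history after infection but different entry dates would be measured over different stretches of it, and both results would carry the same label. What is at stake is whether a primary endpoint is computed as defined. No test or decision rule depends on it.

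**Working it through.** The plan gives no figure to reproduce, so this is date arithmetic.

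**Inputs and assumptions**
- Day 0 is RSV2004 randomization, so the 2-year window is days 0 to 730 (731 days).
- Entry is on day d, with consent the same day. The earliest d is 28 (27 if randomization is called Day 1). The latest is 3 months, taken as 91 days.
- Under the protocol, Month 24 is day d + 730. The visit window is ±7 days; this is legible for the earlier visits and assumed for Month 24.
- The documents fix no infection date. SAP 4.1 categories put symptom onset up to 5 days before randomization.

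**Overrun for a completer, protocol schedule**

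Denominator = (d + 730) − d + 1 = 731. Days past the window = (d + 730) − 730 = d. Days inside it = 731 − d.

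| Entry | Days past 2 years | Share of denominator | Days inside | With ±7 days |
|---|---|---|---|---|
| Day 28 | 28 | 28/731 = 3.8% | 703 | 21/724 = 2.9% to 35/738 = 4.7% |
| 3 months | 91 | 91/731 = 12.4% | 640 | 84/724 = 11.6% to 98/738 = 13.3% |

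Counting from symptom onset instead adds up to 5 days: 33 and 96 days on the nominal visit day.

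**Overrun, SAP 1.2 schedule**

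Month 24 is day 730 ± 7, so the overrun is at most 7 days: 7/710 = 1.0% (Day 28 entry) or 7/647 = 1.1% (3-month entry). From symptom onset it is at most 7 + 5 = 12 days.

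**Effect on the reported percentage**

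Error = (d/731) × (wheezing rate after 2 years − rate within 2 years). It is zero when the rates are equal. A 1-point error needs a difference of 1/0.0383 = 26 points at Day 28 entry, or 1/0.1245 = 8 points at 3-month entry.

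Illustration, assuming 10% wheezing days inside the window and 0% to 20% after it:
- Day 28 entry: (0.10 × 703 + 0 to 0.20 × 28)/731 = 9.6% to 10.4%, still reported as 10.
- 3-month entry: (0.10 × 640 + 0 to 0.20 × 91)/731 = 8.8% to 11.2%, reported as 9 to 11.

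The documents give neither entry dates nor wheezing rates, so these are ranges.

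**The start of the window**

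The denominator opens at consent, so the first 28 to 91 days after randomization lie outside it. The days inside cover 703/731 = 96.2% or 640/731 = 87.6% of the 2 years. Part of the gap is covered by recall at entry (Protocol 9.1.2): back to Day 14 if entry is on Day 28, otherwise up to 30 days. If those days were added to the numerator and every one had wheezing, the result would rise by 14/731 = 1.9 or 30/731 = 4.1 points. At an assumed 10% rate it would rise by 0.2 or 0.4 points.

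**The case against.** The strongest reply is that the SAP has its own consistent timeline. Section 1.2 dates visits from randomization, and Section 2.5 numbers reports by time since the RSV event. On that timeline the last visit falls close to 2 years after infection and the overrun almost disappears. This stands as a reading, and it is why the main finding is conditional on the protocol schedule. It does not remove the point. The formula uses the actual completion date, not a report number, and the SAP itself says it is to be read with the protocol, which counts Month 24 from entry. The documents disagree and do not show which schedule governed the actual visits.

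A second reply is that the label is shorthand for the planned 24-month follow-up. Table 2 uses it that way for the episode count. The two-part objective tells against this for the primary endpoint, although relabelling is a legitimate remedy.

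A third reply is that the consequence is slight. That stands. A percentage is unaffected by extra days at the same rate, a child who leaves before 2 years has no overrun, and the analysis is descriptive in 7 subjects with no extension (SAP 2.4 and 3).

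Some stronger readings are tempting but unsupported:
- **Bias between lumicitabine and placebo.** Nothing in the documents links entry delay to treatment.
- **Asthma computed wrongly.** The definition states the limit, and the sentence about the final visit can be read as only naming the source questionnaires. This is a wording gap.
- **Recalled days inflate the numerator.** The SAP does not say whether they count. The phase start in Table 1, the episode definition in Table 2 and the separate naming of Screening in Table 3 all point to consent as the lower bound.
- **Early days are never observed.** Entry recall covers some of them.

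**Conclusion.** The point holds as a minor defect in a primary endpoint definition. Read with the protocol schedule, SAP 5.1.1 does not compute the period it names. For completers it counts about 28 to 91 days beyond 2 years after randomization, 3.8% to 12.4% of the denominator. Read with SAP 1.2, the overrun is about 1%. The unreconciled visit anchors are therefore part of the finding.

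The effect on any child's percentage is likely to be a point or so at most unless wheezing changes sharply after 2 years, and no inference is altered. The figures rest on randomization as the infection anchor, consent on the day of entry, and completion at the scheduled Month 24 visit.

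A reader might infer that an end cut would make the figure match its label. It would not: the cut corrects the end of the window, while the start remains at entry.

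**What to change.** 1. Count numerator and denominator over the same calendar days, from RSV2002 consent to the earlier of last contact and 2 years after a stated infection anchor. RSV2004 randomization is one candidate. List later days separately, and state that recalled days before consent are not counted.
2. State that the days between infection and entry are outside the denominator, that entry-visit recall covers only part of them, and that window length therefore varies with entry date.
3. If the sponsor prefers to keep the full 24 months, relabel that figure as wheezing during RSV2002 follow-up and report the cut version as the protocol-defined endpoint.
4. Apply the same end date to the asthma diagnosis date and the 2-year episode count. Align the existing Month 24 limit for eczema and allergic rhinitis to it.
5. Reconcile the visit anchor in SAP 1.2 and the report numbering in SAP 2.5 with Protocol 9.1.3 and the Time and Events Schedule.

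**Cost.** SAP wording and a date filter. No new data are needed, because the questionnaire in Protocol Attachment 2 already records dated wheezing days (Section A) and the asthma diagnosis date (Section B). The downside is that, under the protocol schedule, about 28 to 91 observed late days per completer leave the primary figure. Completers' denominators would also vary with entry date, about 703 versus 640 days, where the present formula gives about 731 for each.

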## 3. STUDY DESIGN AND RATIONALE

### 3.1. Overview of Study Design

This is a global multicenter, blinded, LTFU study to evaluate the incidence of the clinical diagnosis of asthma and the frequency of wheezing in infants and children (otherwise healthy or with underlying comorbidities for severe RSV) who have completed their treatment course and their last planned study-related visit in a previous Phase 2 study, 64041575RSV2004, in which they received lumicitabine or placebo for the treatment of RSV infection. Subjects will be followed for at least 2 years following treatment. Participation in this LTFU study is optional for study sites. This LTFU study will be offered to subjects of Study 64041575RSV2004 if their site decides to participate in the LTFU.

No study drug will be administered in this study. Subjects may be enrolled within 3 months after randomization in Study 64041575RSV2004. Assessments will be performed at the time points specified in the [Time and Events Schedule](#). The last visit of Study 64041575RSV2004 (ie, Day 28) may be combined with the entry visit of this LTFU study.

Parents/caregivers will be provided with a wheezing parent/caregiver card and a medication parent/caregiver card, both of which should be completed on a daily basis. These parent/caregiver cards will serve as reminder cards when a study site responsible person interviews the subject’s parent/caregiver in order to complete a standardized paper questionnaire. The questionnaire will be completed by a study site responsible person at each study site visit as noted in the [Time and Events Schedule](#) and during a monthly telephone call (calendar month  $\pm 7$  days) between study site visits (see Section 9.1.3).

An unblinded interim analysis will be performed when all subjects from the first season in Study 64041575RSV2004 who are enrolled in this LTFU study complete the 18 months follow-up assessment of this LTFU study. Sites and the parents/caregivers of subjects will remain blinded. This interim analysis will serve to evaluate the need for an extension of the follow-up period (see Section 11.6).

The planned total study duration for each subject will be 24 months unless the decision is taken to extend the duration of follow-up in this study, based on the interim analysis.

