2.4. Definition of Subgroups and Subsets

As study 64041575RSV2002 only included 7 subjects, no subgroups or subsets will be defined.

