3. INTERIM ANALYSIS

An unblinded interim analysis was to be performed when all subjects from the first season in Study 64041575RSV2004 who are enrolled in this LTFU study complete the 18-month follow-up assessment of this LTFU study. This interim analysis was to serve an evaluation of the need for an extension of the follow-up period. The interim analysis was not performed as the project was stopped and due to the limited sample size, an extension of the follow-up period was not deemed useful for the objectives of this trial.

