5.1.3. Analysis Methods

The proportions of subjects with clinical diagnosis of asthma within the first 2 years after the RSV infection will be presented descriptively by previous treatment group, together with the 95% (2-sided) confidence intervals using the Wilson method.

The percentage of days with wheezing within the first 2 years after the RSV infection will be presented descriptively by previous treatment group, including 95% CIs.

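### SAP 5.1.1 rounds each child's 2-year wheezing percentage to a whole number before analysis, so about 1 to 3 wheezing days over full follow-up score 0% (low severity)

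*SAP*

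**What the plan says.** SAP 5.1.1 introduces the endpoint with "The percentage of wheezing days in a subject within the first 2 years after the RSV infection will be calculated as" and gives the formula: wheezing days over (day of study completion minus day of informed consent plus 1), times 100. The next sentence is "The percentage will be rounded to the nearest integer". The numerator is a whole-day count: "Number of wheezing days is the sum of all days that were reported in the Monthly visit reports". The denominator starts at entry to this study: "The day of informed consent is the informed consent of the RSV2002 study".

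SAP 5.1.3 states how the value is used: "The percentage of days with wheezing within the first 2 years after the RSV infection will be presented descriptively by previous treatment group, including 95%" confidence intervals. It does not say whether the rounded or the unrounded value enters the summary.

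Protocol 2.1.2 and 11.3.1 define the same endpoint per subject with no rounding step. On length of follow-up, Protocol 3.1 says "The planned total study duration for each subject will be 24 months unless the decision is taken to extend", and SAP 3 records that "an extension of the follow-up period was not deemed useful for the objectives of this trial". The sample is given in SAP 2.4: "As study 64041575RSV2002 only included 7 subjects, no subgroups or subsets will be defined".

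**The concern.** The rounding sentence sits in the definition, directly after the formula. It is not in a rule on table format. The SAP puts rounding inside other derivations too (BMI in 4.1, the monthly wheezing percentage in Table 2, days missed from work in Table 3). A programmer who follows the text would therefore most naturally store an integer and analyse it.

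The parents record wheeze every day as 0 or 1 on the card in Protocol Attachment 3. Over about two years one such day is worth roughly 0.14 percentage points, so a whole-percent scale is about seven times coarser than the data. At the bottom of the scale, the primary summary would then be unable to separate a child with no wheeze from a child with a few days of it. A child's score could also cross from 0% to 1% because follow-up was shorter, with no change in the number of wheezing days.

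**Working it through.** The plan gives no worked percentage, power or sample size figure for this endpoint, so there is nothing to reproduce. The check applies the SAP 5.1.1 formula directly.

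**Inputs**
- k = number of wheezing days (SAP 5.1.1).
- D = completion day − consent day + 1 (SAP 5.1.1). For 24 months, D = 730 + 1 = 731, assuming 730 days elapsed.
- The ±7-day visit window in the Time and Events Schedule gives D = 724 to 738.
- SAP 1.2 counts visits from randomization in the parent study, whereas the protocol counts them from the entry visit. With entry up to 3 months after randomization (taken as 91 days), D could be as low as 731 − 91 = 640.
- For early withdrawal at about 6, 12 and 18 months, D = 183, 366 and 549. This assumes that the day of study completion then means the last day in the study.

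**Formula:** score = 100 × k / D, rounded to the nearest integer (halves up).

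| D (days) | k = 1 | k = 2 | k = 3 | k = 4 |
|---|---|---|---|---|
| 731 | 0.137 → 0 | 0.274 → 0 | 0.410 → 0 | 0.547 → 1 |
| 640 | 0.156 → 0 | 0.312 → 0 | 0.469 → 0 | 0.625 → 1 |
| 549 | 0.182 → 0 | 0.364 → 0 | 0.546 → 1 | 0.729 → 1 |
| 366 | 0.273 → 0 | 0.546 → 1 | 0.820 → 1 | 1.093 → 1 |
| 183 | 0.546 → 1 | 1.093 → 1 | 1.639 → 2 | 2.186 → 2 |

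**Width of the bins at D = 731.** Counts of 0 to 3 days score 0%, 4 to 10 days score 1%, and 11 to 18 days score 2%. The cut between 3 and 4 days is the same at D = 724 and D = 738.

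**Range over which exactly 1 to 3 days collapse to 0%.** Three days score 0 when 300 / D < 0.5, that is D > 600. Four days score 1 when 400 / D ≥ 0.5, that is D ≤ 800. So the statement holds for D from 601 to 800.

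**Effect of length of follow-up.** Three wheezing days give 0.410% at D = 731 and 0.546% at D = 549. A percentage should differ with its denominator, but the true gap is 0.546 − 0.410 = 0.136 points, and the scored gap is 1 point (0% against 1%).

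**Largest error.** Rounding to the nearest integer moves a value by at most 0.5 points. At D = 731 that is 0.005 × 731 = 3.66, or about 3.7 days.

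**Monthly percentage in Table 2, for comparison.** One day in a 31-day month is 100 / 31 = 3.2%, and in a 28-day month 100 / 28 = 3.6%. These score 3% and 4%. Each further day adds more than 3 points, so every day count keeps its own score and none falls to 0.

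**The case against.** The strongest reply is that little depends on this. The analysis is descriptive, no hypothesis is tested, the study has 7 children, and the project was stopped with no interim or extension decision left. An error of at most 0.5 points per child will probably be small beside the sampling uncertainty in 7 children, though the documents give no standard deviation to confirm it. The information is also not lost from the report. SAP 5.2.2 provides listings of reported wheezing with the derived parameters. Table 2 counts episodes of one day or more, and it gives monthly percentages in which a single day is visible. This stands, and it sets the severity.

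It can also be said that SAP 5.1.1 and 5.1.3 never state that means and intervals are computed from the rounded values. That is true. Placement in the definition makes it the natural reading, but a sentence limiting the rounding to display would resolve it.

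A reader might infer more than the documents support:
- **That rounding biases the group means or produces zero-width intervals.** It works in both directions: at 731 days, 4 to 7 wheezing days round up and 8 to 10 round down. A zero-width interval needs every child in an arm to fall in one bin. Four children with 3, 3, 2 and 1 days would do it (true mean 2.25 / 731 = 0.31%, rounded mean 0 with no spread). But that is a chosen worst case, and the documents do not give the split of the 7 children by arm.
- **That most children would have only a few wheezing days, where a treatment effect would show.** Neither document gives an expected number or distribution of wheezing days. If children wheeze on tens of days, the rounding is negligible.
- **That the monthly percentage in Table 2 needs the same repair.** The arithmetic above shows that it does not.

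**Conclusion.** The point holds, at low severity. As written, SAP 5.1.1 makes integer rounding part of a primary endpoint's derivation, a step the protocol definition does not contain. For a child followed for 601 to 800 days, which includes the planned 24 months, 1 to 3 wheezing days become 0% and cannot be told apart from none in the primary summary. Below 601 days fewer day counts collapse, so the same count can score differently by length of follow-up.

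The conclusion rests on a denominator near 731 days for a completed child and on the natural reading that the rounded value is the one analysed in 5.1.3. The rule does not hide who wheezed from the report as a whole, and it does not put the descriptive conclusions of the study at risk. Its effect is on the primary summary, mainly in an arm where wheeze is rare.

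**What to change.** In SAP 5.1.1, delete the rounding sentence or restrict it to display. State that all summary statistics and confidence intervals in 5.1.3 are computed from the unrounded per-subject percentages. Display the percentage to at least one decimal, and print the raw number of wheezing days beside it in the listing. At 731 days one decimal already separates 0, 1, 2 and 3 days (0.0, 0.1, 0.3, 0.4). Leave the monthly percentage in Table 2 as it is.

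The cost is one or two sentences in the SAP and the matching line of programming. No new data are needed, and the documents state no benefit of rounding that would be lost.
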